6.2 SAFETY POPULATION

The Safety Population will consist of all participants who received at least 1 administration of study intervention. Participants will be summarized according to the study intervention received.

7.0 PATIENT DISPOSITION

Participant disposition encompasses the distribution of participants screened, randomized, treated, and who completed or discontinued the study (along with reasons for withdrawal/discontinuation). Participant disposition will be summarized for all screened participants in total and by study intervention group.

8.0 DEMOGRAPHICS AND OTHER BASELINE CHARACTERISTICS

8.1 DEMOGRAPHICS AND BASELINE CHARACTERISTICS

Demographic parameters (age; age group; sex; race; ethnicity), baseline characteristics (weight; height; body mass index, calculated as weight [kg]/(height [m])²; baseline MMPS and MMPS-P) will be summarized descriptively for the mITT Population by study intervention group and in total. Continuous variables will be summarized by number of participants and mean, SD, median, minimum, and maximum values. Categorical variables will be summarized by number and percentage of participants.

8.2 MEDICAL HISTORY

Medical history, encompassing abnormalities and surgeries reported as occurring before Day 1, will be coded using the Medical Dictionary for Regulatory Activities (MedDRA), version 22.0 or newer. Unique participants who report medical history events will be summarized by MedDRA system organ class (SOC) and preferred term (PT) for the mITT Population by study intervention group. Medical history will be summarized separately for those ongoing at Day 1 and those not ongoing at Day 1.

8.3 PRIOR AND CONCOMITANT MEDICATIONS

Medications will be coded using the World Health Organization (WHO) Drug Dictionary. Prior medications are medications taken ≥ 1 time before the study intervention start date, regardless of medication end date. Concomitant medications are medications taken ≥ 1 time on or after the study intervention start date, regardless of medication start date. Unique participants who reported medications will be summarized by WHO Drug class and preferred drug name for the mITT Population by study intervention group. Prior and concomitant medications will be summarized separately.

9.0 EFFICACY ANALYSES

The efficacy analyses will be based on the mITT Population, defined as randomized participants with at least 1 postbaseline MMPS assessment. The last-observation-carried-forward approach will be used to impute missing postbaseline values. *Baseline* for efficacy is defined as the last approved non-missing efficacy assessment before the first dose of study intervention. Pairwise comparisons will be conducted between each BOTOX group and the placebo group. All statistical tests will be 2-sided hypothesis tests performed at the 5% level of significance for main effects. All confidence intervals will be 2-sided 95% confidence intervals, unless stated otherwise.

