4.3. Justification for Dose

In Allergan's Phase 2 Study 191622-130, participants received total doses ranging from BOTOX 24 U to 96 U. For the primary and key secondary endpoints (at Day 90), statistically significant positive efficacy results were demonstrated for all 4 BOTOX doses, with a dose-dependent trend favoring the higher 3 doses (48 U, 72 U, and 96 U), which produced statistically significant changes in MMP compared with placebo. The benefits of 72 U and 96 U were similar for duration (approximately 9 months for Kaplan-Meier median time to loss of 1-grade MMPS response), volume reduction, MMPS Grade change, facial width, facial angle, and facial shape. There was no additional benefit demonstrated with 96 U over 72 U. Statistically significant efficacy results were also obtained with the 24 U dose versus placebo for the majority of endpoints evaluated, though not all. However, the Kaplan-Meier duration of effect based on median time to loss of MMPS 1- or 2-grade improvement was approximately 3 to 7 weeks shorter in the BOTOX 24 U group than the BOTOX 48 U group.

The proportion of responders achieving a rating of \leq 3 (moderate) on the MMPS was significantly greater with all BOTOX doses compared with placebo (p < 0.008), with the greatest impact shown in the 48 U (83.3%), 72 U (89.5%), and 96 U (89.5%) dose groups at Day 90.

Participants treated with BOTOX experienced significant reductions in lower facial volume (cm³) at Day 90 compared with placebo (p < 0.001), with the greatest mean reductions shown in the 3 highest BOTOX dose groups of 48 U (-6.84 cm³), 72 U (-7.41 cm³), and 96 U (-8.20 cm³).

The responder rate for achieving a 2-grade improvement from baseline using the MMPS was significantly greater with all BOTOX doses compared with placebo (p < 0.001), with the greatest proportion of responders in the 72 U (73.7%) and the 96 U (65.8%) dose groups at Day 90; the proportion of responders in the 48 U dose group was 47.2%.

BOTOX administration was shown to be safe through Day 360 for all doses (24 U, 48 U, 72 U, and 96 U). Facial paresis (including reports of weak or altered smile) was reported in the highest dose group (96 U) as a local effect.

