9.1. Statistical Hypotheses

The following set of hypotheses will be used to compare the BOTOX groups with placebo:

- Null hypothesis: BOTOX and placebo are equally effective in reducing MMP as measured by the proportion of responders achieving MMPS Grade ≤ 3 at Day 90.
- Alternative hypothesis: BOTOX and placebo are not equally effective in reducing MMP as measured by the proportion of responders achieving MMPS Grade ≤ 3 at Day 90.

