9.2. Sample Size Determination

The primary efficacy parameter is the proportion of responders who achieve MMPS Grade \leq 3 at Day 90. Based on previous data from Study 191622-130 and the assumption of a difference of \geq 34% in MMPS responder rate between BOTOX 48 U or 72 U and placebo group, approximately 50 participants per study intervention group will provide > 90% power using a 2-sided Mantel-Haenszel test, 10% dropout rate, and 5% significance level.

Approximately 225 participants will be screened to achieve 150 enrolled to study intervention and 135 evaluable participants for an estimated total of 45 evaluable participants per intervention group.

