9.4.1.2. Primary Analyses

The primary efficacy endpoint will be the proportion of responders who achieve MMPS Grade \leq 3 at Day 90 and will be analyzed using Cochran-Mantel-Haenszel model stratified by baseline MMPS Grade (4 or 5). Each BOTOX dose will be compared with placebo separately.

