9.1 PRIMARY EFFICACY PARAMETER

The primary efficacy variable is the investigator's assessment of MMP using the MMPS (1 = minimal, 2 = mild, 3 = moderate, 4 = marked, 5 = very marked). Each participant's MMPS score will be based on the worst score of the left and right side of the face. If a score is missing for 1 side of the face, then the participant's MMPS score will be based on the score for the other side of the face. The primary efficacy endpoint will be the proportion of responders who achieve MMPS Grade ≤ 3 at Day 90.

The following set of hypotheses will be used to compare the BOTOX groups with placebo:

- Null hypothesis: BOTOX and placebo are equally effective in reducing MMP as measured by the proportion of responders achieving MMPS Grade ≤ 3 at Day 90.
- Alternative hypothesis: BOTOX and placebo are not equally effective in reducing MMP as measured by the proportion of responders achieving MMPS Grade \leq 3 at Day 90.

Frequency counts of participants achieving a MMPS Grade \leq 3 will be tabulated by study intervention group at each postbaseline visit. The difference between each BOTOX dose and placebo in the proportion of participants with MMPS \leq 3 will be analyzed using Cochran-Matel-Haenszel (CMH) model stratified by baseline MMPS Grade (4 or 5).

A sensitivity analysis will be performed based on all observed data for the mITT Population.

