12.0 DETERMINATION OF SAMPLE SIZE

The primary efficacy parameter is proportion of responders who achieve MMPS Grade \leq 3 at Day 90 (last observation carried forward). Based on previous data from study 191622-130 and the assumption of \geq 34% difference in MMPS response rate between BOTOX 48 U or 72 U and placebo and 10% dropout rate, approximately 50 participants will provide > 90% power using a 2-sided Mantel-Haenszel test at 5% significance level.

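### Do two BOTOX doses, each tested against the same placebo arm at two-sided 5%, need a multiplicity rule?

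*SAP*

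**What the plan says.** SAP 9.0 fixes the contrasts: "Pairwise comparisons will be conducted between each BOTOX group and the placebo group". The same section gives the error level: "All statistical tests will be 2-sided hypothesis tests performed at the 5% level of significance for main effects". Protocol 9.4.1.2 agrees on the structure: "Each BOTOX dose will be compared with placebo separately".

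Both documents then give one null and one alternative, worded for BOTOX in general. SAP 9.1 introduces them with "The following set of hypotheses will be used to compare the BOTOX groups with placebo", and Protocol 9.1 begins "Null hypothesis: BOTOX and placebo are equally effective in reducing MMP".

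The sample size rests on one dose against placebo at 5%. Protocol 9.2 assumes a difference of at least 34 points for 48 U or 72 U and says that about 50 per group "will provide > 90% power using a 2-sided Mantel-Haenszel test, 10% dropout rate, and 5% significance level". SAP 12.0 matches: "approximately 50 participants will provide > 90% power using a 2-sided Mantel-Haenszel test at 5% significance level".

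Neither document names a multiplicity procedure, and the SAP table of contents has no section for one. For the secondary endpoint of lower facial volume, Protocol 9.4.1.3 and SAP 9.2 plan the same ANCOVA for two area-of-interest (AOI) methods, landmark and statistical. Neither is designated as the main analysis.

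**The concern.** Two p-values bear on one generically worded null. If only one dose falls below 0.05, the text does not say outright whether that null is rejected. Someone who counts a win on either dose as a positive trial runs two chances of a false positive, and the error of that reading is nearly double that of one test. A rule chosen after unblinding could be picked to suit the results, so the time to settle it would be before database lock.

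The two volume methods raise the same question on a smaller scale: a significant result on only one of them has no stated status.

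**Working it through.** **Inputs.** Two-sided 5% per test (SAP 9.0). Two comparisons sharing one placebo arm, allocated 1:1:1 (Protocol 4.1). A 34-point difference, 50 per arm, 10% dropout and 45 evaluable per arm (Protocol 9.2). The documents do not give the placebo responder rate. Protocol 4.3 gives active rates from the earlier study, "with the greatest impact shown in the 48 U (83.3%), 72 U (89.5%), and 96 U (89.5%) dose groups at Day 90", so a 34-point difference implies placebo rates of 83.3 − 34 = 49.3% and 89.5 − 34 = 55.5%. The assumed range is 33% (least favourable for power) to 55.5%.

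**1. The plan's own figure.** Dropout: 45 / 0.90 = 50. For one dose against placebo, with p̄ the mean of the two rates:

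power = Φ{[0.34 − 1.96·√(2p̄(1−p̄)/45)] / √[(p₀(1−p₀) + p₁(1−p₁))/45]}

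- 33% vs 67%: (0.34 − 1.96 × 0.1054) / 0.0991 = 1.35, so 91.1%. This is the minimum over placebo rates of 1% to 60%.
- 49.3% vs 83.3%: 94.0%.
- 55.5% vs 89.5%: 96.3%.

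The stated power above 90% reproduces at 5% per test.

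**2. Familywise error when both doses are inert.** Each difference has variance 2σ²/n, and the shared placebo mean contributes covariance σ²/n, so the correlation is 0.5. From the bivariate normal:

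- 1 − P(|Z₁| < 1.96, |Z₂| < 1.96) = 9.07%
- 1 − P(Z₁ < 1.96, Z₂ < 1.96) = 4.54%, against 2.5% for one test

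Simulated Mantel-Haenszel tests stratified by baseline grade, with assumed strata and 45 or 50 per arm, give 8.3% to 9.9% and 4.1% to 5.0%. An unstratified test at 50 per arm can reach 10.3%. That excess comes from discreteness: at responder rates of 45% to 55.5% the size of a single such test is already about 5.5% to 5.7%. Two tests of exactly 5% cannot exceed 10% together.

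**3. When one dose works.** Only one true null is left. Its error is the nominal 5%, or 2.5% in favour of BOTOX.

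**4. Price of a familywise rule.** Under Hochberg both doses are significant if both p ≤ 0.05; otherwise the smaller p must be ≤ 0.025. Power for a dose with the 34-point effect, unstratified Mantel-Haenszel test, 45 per arm:

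| Placebo rate (assumed) | Unadjusted | Hochberg, other dose 34 points | Other dose 20 points | Other dose no effect |
|---|---|---|---|---|
| 33% | 90.2% | 89.3% | 86.8% | 86.1% |
| 45% | 92.2% | 91.3% | 88.2% | 87.7% |
| 49.3% | 94.1% | 93.4% | 90.5% | 89.9% |
| 55.5% | 96.6% | 96.2% | 94.2% | 94.0% |

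The loss is about 1 point or less when both doses work, and about 2.4 (96.6 − 94.2) to 4.5 (92.2 − 87.7) points otherwise. With the other dose inert, power is below 90% at placebo rates of 33%, 45% and 49.3%. With Hochberg and both doses inert, the two-sided familywise error is 4.3% to 5.0%.

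**5. Two volume methods, one dose.** The chance that at least one method is falsely significant is 8.3%, 7.8% or 7.0% if their test statistics correlate 0.7, 0.8 or 0.9. These correlations are assumed; the documents give none.

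**The case for a change.** The best argument for a change is that the protocol sets out formal hypotheses and powers them, so its decision rule ought to be complete. The single generic null can be read as one claim supported by either dose, and on that reading the 9% applies. A rule costs only wording and must be fixed before unblinding.

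Part of this stands. The arithmetic is right, no joint rule appears in the readable text, and one added sentence would remove doubt. Some SAP text is missing from the public copy, but Sections 9.0, 9.1 and 12.0, where a rule would sit, are readable.

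The rest is weaker. Separate comparisons, a 5% level for each, and a sample size built on either dose against placebo at 5% all point to two dose-specific decisions. On that reading, one dose below 0.05 and one above is not an undefined outcome: the null is rejected for that dose only. The 9% also needs both doses to be inert, whereas Protocol 4.3 reports that both beat placebo on this endpoint in the earlier study (p < 0.008). Error control must still cover the inert case, but it is the least expected one here.

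On volume, Protocol 10.7.2 presents the statistical AOI as additional and the landmark AOI as the method carried over from the earlier study. That suggests an order without fixing one. Both results are reported in any event, so a label would alter no estimate or p-value.

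**Conclusion.** No change to the plan is needed. Testing each dose at two-sided 5% is correct per comparison and agrees with how the study was sized. The 9.07% (4.54% in favour of BOTOX) is a true property of one particular reading: both doses inert and a win on either counted as success. It contradicts nothing in the documents, which promise no familywise control.

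Hochberg is a legitimate alternative. It buys that control with up to about 4.5 points of power per dose and can miss the stated 90% target, depending on a placebo rate the documents do not give (assumed 33% to 55.5%) and on the other dose's effect. In Phase 2b that exchange is a matter of judgement. The power statement holds at 5% per test, so it needs no restating unless an adjustment is adopted. Calling the secondary p-values nominal, or one volume method supportive, would change no reported result. A report that gives both doses' results and interprets each separately loses nothing.

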9.1 PRIMARY EFFICACY PARAMETER

The primary efficacy variable is the investigator's assessment of MMP using the MMPS (1 = minimal, 2 = mild, 3 = moderate, 4 = marked, 5 = very marked). Each participant's MMPS score will be based on the worst score of the left and right side of the face. If a score is missing for 1 side of the face, then the participant's MMPS score will be based on the score for the other side of the face. The primary efficacy endpoint will be the proportion of responders who achieve MMPS Grade ≤ 3 at Day 90.

The following set of hypotheses will be used to compare the BOTOX groups with placebo:

- Null hypothesis: BOTOX and placebo are equally effective in reducing MMP as measured by the proportion of responders achieving MMPS Grade ≤ 3 at Day 90.
- Alternative hypothesis: BOTOX and placebo are not equally effective in reducing MMP as measured by the proportion of responders achieving MMPS Grade \leq 3 at Day 90.

Frequency counts of participants achieving a MMPS Grade \leq 3 will be tabulated by study intervention group at each postbaseline visit. The difference between each BOTOX dose and placebo in the proportion of participants with MMPS \leq 3 will be analyzed using Cochran-Matel-Haenszel (CMH) model stratified by baseline MMPS Grade (4 or 5).

A sensitivity analysis will be performed based on all observed data for the mITT Population.

9.2 SECONDARY EFFICACY PARAMETERS

The following are considered secondary endpoints at Day 90:

- Proportion of responders who achieve MMPS-P Grade ≤ 3
- Proportion of responders who achieve \geq 2-grade MMPS improvement from baseline

- Proportion of responders who achieve \geq 2-grade MMPS-P improvement from baseline
- Proportion of responders who achieve PSAC Grade ≥ 2 (at least moderately improved from baseline)
- Change from baseline in lower facial volume by VECTRA M3 measured using landmark area of interest (AOI) and statistical MMP AOI

For all the responder analyses, frequency counts of responders for each of the responder definitions above will be tabulated by study intervention group at each postbaseline visit. The difference between each BOTOX dose and placebo in the proportion of responders will be analyzed using CMH model stratified by baseline MMPS Grade (4 or 5).

The change from baseline in lower facial volume using both landmark AOI and statistical MMP AOI will be analyzed using analysis of covariance (ANCOVA) with study intervention and investigator site as factors and baseline MMPS Grade (4 or 5) as a covariate. Missing values for change from baseline in lower facial volume at Day 30 will be imputed using the average of participants with non-missing values.

Summary statistics for each endpoint will be tabulated by study intervention group at each postbaseline visit.

Each of the responder analyses will be analyzed using CMH model stratified by baseline MMPS grade.

The change from baseline analyses will be analyzed using ANCOVA with study intervention and investigator site as factors and baseline MMPS grade and baseline score as covariates.

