8.1.2. Secondary Efficacy Assessments

MMPS-P and lower facial volume assessments will be completed at screening, baseline, and at each scheduled visit thereafter until study exit. The PSAC will be completed at all scheduled postbaseline visits (Days 30, 60, 90, 120, 150, and 180). Participants will view a training video on how to properly complete the MMPS-P and PSAC assessments using photos, at the Screening Visit (and at other visits if needed).

For MMPS-P and PSAC, the participant will answer questions via electronic tablet that will be provided to the study participant at the study site.

MMPS-P

MMP assessed by the participant is a secondary efficacy assessment developed by the sponsor through concept elicitation and cognitive debriefing in accordance with the FDA Patient Reported Outcomes guidance. Participants will be asked to assess the severity of their masseter prominence using a single question composed of 5 severity grades (1 = not at all pronounced, 2 = mildly pronounced, 3 = moderately pronounced, 4 = pronounced, 5 = very pronounced; see Appendix 8 for details) and a 2D image of their face collected at the current visit.

The MMPS-P is evaluated for both masseters as a single score.

Evaluations of MMPS-P completed at screening and baseline will be used for test-retest reliability assessment of the tool.

PSAC

The PSAC is a commonly used assessment of change scale that has been adapted for use with MMP by the sponsor using concept elicitation and cognitive debriefing. Participants will be asked to assess change of their lower face shape using images taken before study intervention (ie, baseline, or screening if the baseline image is not of acceptable quality) and after study intervention (ie, the current study visit) taking into consideration the bottom half of the face from the top of the cheeks to the chin. The PSAC grades are as follows: 3 = much improved, 2 = moderately improved, 1 = minimally improved, 0 = change, -1 = minimally worse, -2 = moderately worse, and -3 = much worse (see Appendix 8 for details).

Lower Facial Volume

Lower facial volume will be calculated by a qualified technician (from Canfield Scientific, Inc.) using 3D image models using 2 analysis methods.

Investigators will follow training/instructions for use of the digital imaging system as provided by Canfield Scientific, Inc.

[figure not shown]

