9.4.1.3. Secondary Analyses

The following secondary variables will be analyzed at Day 90 using the same method as the primary analysis:

- Proportion of responders who achieve MMPS-P Grade ≤ 3
- Proportion of responders who achieve ≥ 2-grade MMPS improvement from baseline
- Proportion of responders who achieve ≥ 2-grade MMPS-P improvement from baseline
- Proportion of responders who achieve PSAC Grade ≥ 2

The change from baseline in lower facial volume at Day 90 (calculated from standardized images and analyzed by 2 methods) will be statistically analyzed using ANCOVA with study intervention group and investigator sites as factors and baseline MMPS Grade (4 or 5) as a covariate.

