6.1 MODIFIED INTENT-TO-TREAT POPULATION

The modified Intent-to-Treat (mITT) Population will consist of all randomized participants with at least 1 postbaseline MMPS assessment. Participants will be summarized according to the randomized study intervention.

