14.0 DATA HANDLING CONVENTIONS

14.1 VISIT TIME WINDOWS

Table 14-1 presents the visits assigned for efficacy and safety analyses and the corresponding range of study intervention days (window) during which an actual visit may occur.

Derived Visit	Scheduled Visit Day ^a	Window	
Baseline	Day 1	$Days \le 1$	
Day 30	Day 30	Days [2, 45]	
Day 60	Day 60	Days [46, 75]	
Day 90	Day 90	Days [76, 105]	
Day 120 Day 120		Days [106, 135]	
Day 150	Day 150	Days [136, 165]	
Day 180	Day 180	$Days \ge 166$	
End of Study ^b	Final or Termination Visit during the double-blind treatment period		

Table 14-1Visit Time Windows

a Relative to the date of the first dose of study intervention. Day 1 = the date of the first dose of study intervention. There is no Day 0.

b Presented in analysis tables for safety parameters, including but not limited to vital signs.

If the assessment date is on or after the date of the first dose of study intervention, the study day is calculated by assessment date – date of the first dose of study intervention + 1. If the assessment date is before the date of the first dose of study intervention, the study day is calculated by assessment date – date of the first dose of study intervention. Therefore, a negative day indicates a day before the start of the study intervention. If the assessment date is unavailable, use the visit date instead.

If a participant has 2 or more visits within the same window, the last visit with a nonmissing value will be used for analysis.

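### The SAP fills missing Day 30 lower facial volume with an average of unspecified scope: pooled it dilutes the difference, by arm it understates the standard error, and its use in LOCF is undefined

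*SAP*

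**What the plan says.** SAP 9.2 lists change in lower facial volume as a secondary endpoint at Day 90, measured by two area-of-interest methods. The model is an ANCOVA with treatment and site as factors and baseline MMPS grade as covariate. The section then adds: "Missing values for change from baseline in lower facial volume at Day 30 will be imputed using the average of participants with non-missing values". It does not say whether the average runs over all participants or within arm, and it gives no multiple imputation or variance correction.

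The general rule in SAP 9.0 is different: "The last-observation-carried-forward approach will be used to impute missing postbaseline values". Protocol 9.4.1 has the same LOCF rule and does not mention a mean fill.

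Four other places bear on the point:

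- Protocol 8.1.2: "MMPS-P and lower facial volume assessments will be completed at screening, baseline, and at each scheduled visit thereafter until study exit". Day 30 is therefore the first scheduled postbaseline volume, and LOCF has no earlier postbaseline value to carry to it.
- SAP 6.1 defines the mITT population as "all randomized participants with at least 1 postbaseline MMPS assessment". A usable image is not required.
- SAP 14.1, for several visits in one window: "the last visit with a nonmissing value will be used for analysis". It does not say whether an imputed value counts as nonmissing.
- SAP 9.1, under the primary endpoint only: "A sensitivity analysis will be performed based on all observed data for the mITT Population". No such analysis is stated for volume.

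**The concern.** A single mean fill followed by an ordinary ANCOVA does harm whichever average is meant. If all arms are pooled, every missing participant receives the same value regardless of treatment, so the arms are pulled together. If the average is within arm, the arm means are unchanged, but the filled values add no scatter and still count as participants, so the model overstates its precision.

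There is also a gap in the specification. Two programmers following this SAP could fill Day 30 differently. They could also disagree on whether the filled value is an observation that LOCF may carry to Day 60 and Day 90. The second choice matters for mITT participants who have an MMPS rating but no usable volume through Day 90: a constant could enter the Day 90 secondary endpoint as if it had been measured, under both volume methods.

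**Working it through.** **The plan's own figure.** The documents give no power or sample size for volume. The stated power above 90% concerns the MMPS responder endpoint. It reproduces at 45 evaluable per arm (94.0% for 49.3% vs 83.3%; 96.3% for 55.5% vs 89.5%) and is not touched by this rule.

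**Inputs.**
- From the documents: 50 per arm; 2-sided 5% level; mean Day 90 volume changes in the earlier study of -6.84 cm³ (48 U) and -7.41 cm³ (72 U), Protocol 4.3.
- Assumed, because the documents do not give them: placebo mean -1 cm³; SD 6 cm³ (range 4 to 8); k = 1, 2 or 5 of 50 missing per arm, completely at random. No Day 30 mean is given, so the Day 90 means set the scale and a run with all means halved is added.
- True 72 U difference: -7.41 - (-1) = -6.41 cm³.

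**Day 30, pooled fill.** With missing fraction m = k/50 in every arm and pooled mean g, each filled arm mean is (1 - m) × observed mean + m × g. The g terms cancel, so the difference is multiplied by (1 - m). At 5 of 50: 0.90 × (-6.41) = -5.77.

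**Day 30, by-arm fill.** The difference is unchanged. The model divides the residual sum of squares of 3(50 - k) real values by 150 - 3 degrees of freedom:
- Reported SE = SD × √(2/50) × √[3(49 - k)/147]. At k = 5: 6 × 0.2 × √(132/147) = 1.14.
- True SE = SD × √[2/(50 - k)]. At k = 5: 6 × √(2/45) = 1.26.

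The ratio is 0.90 and does not depend on the SD.

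**Simulation.** 20,000 trials per scenario, three arms, common-variance comparison without site or baseline grade, SD 6:

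| Fill at Day 30 | Missing per arm | Result |
|---|---|---|
| Pooled | 1 of 50 | 95% CI coverage about 95% |
| Pooled | 5 of 50 | estimate -5.78; coverage 91.9%; type I error 4.9% to 5.1% |
| By arm | 1 of 50 | type I error 5.6% |
| By arm | 2 of 50 | type I error 5.9% |
| By arm | 5 of 50 | reported SE 1.14, true 1.26; type I error 7.7% |

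Pooled coverage at 5 of 50 is 87.5% at SD 4, 92.9% at SD 8, and 94.1% if all means are halved (SD 6). Analysis of observed values only is unbiased, with type I error about 5%.

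**Day 90, only if LOCF may carry the fill.**
- Pooled: the carried constant is the same in every arm, so the shrinkage is (k/50) × 6.41 = 0.13, 0.26 or 0.64 cm³ for k = 1, 2 or 5.
- By arm: type I error at 5 of 50 is about 5% to 7.5% as the assumed Day 30 to Day 90 correlation runs from 0 to 0.9; at 1 of 50 it is 4.8% to 5.5%.
- By arm, if the Day 30 effect is half the Day 90 effect: the Day 90 difference also shrinks by (k/50) × 3.2 = 0.06, 0.13 or 0.32 cm³.
- Power was at least 99.8% in every carry-forward run at SD 6.

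**The case against.** The strongest objection is relevance. Volume is a Day 90 endpoint, and no section expressly plans a Day 30 test. The sentence "Summary statistics for each endpoint will be tabulated by study intervention group at each postbaseline visit" may belong to SAP 9.3, which the contents page lists but the available text does not show. That uncertainty is real, but a rule that fills Day 30 values has a purpose only if Day 30 values are reported or used later.

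Second, the literal reading is pooled, which keeps type I error near 5% and biases toward zero. That is fair, and the inflated type I error arises only under the by-arm reading. The pooled reading still gives a biased estimate and an interval that covers too rarely when several values are missing.

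Third, 5 of 50 has no source. The planned 10% dropout does not supply it, because anyone who leaves before a postbaseline MMPS rating is outside the mITT population. The Day 30 window is also wide (Days 2 to 45), and images and MMPS ratings are scheduled at the same visits. This stands: 5 of 50 is an upper illustration, and at 1 of 50 the effects are slight. Few missing values also mean that the rule gains little.

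Fourth, the 99.8% power holds at SD 6 only. At SD 8, a same-visit fill at 5 of 50 gives 96.4% pooled against 96.6% on observed data, so the conclusion is unchanged.

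Fifth, the separate table specifications might settle which average is meant, or one clarifying sentence could. Either would remove the ambiguity, but the chosen reading would still carry its own fault.

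**Conclusion.** The concern holds. The rule names no arm, and with the stated ANCOVA it gives either a diluted Day 30 difference or a standard error that is too small. Whether the fill may reach Day 90 through LOCF is neither stated nor excluded. That filled values are analysed as observed is inferred from the absence of any stated correction.

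The shrinkage factor (1 - m) requires equal missingness across arms. With unequal missingness the difference still shrinks while the pooled mean lies between the placebo and BOTOX means. The standard-error ratio follows from the design and the missing fraction alone. The cm³ figures and coverage rest on the assumed SD, placebo mean, Day 30 effect and number missing.

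The practical weight is moderate: a small to moderate distortion at Day 30, and a probably small effect at Day 90 that is unlikely to change significance. It should be corrected because the result depends on an unstated choice and the correction is cheap.

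**What to change.** In SAP 9.2:

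1. Delete the Day 30 mean-imputation sentence.
2. State that LOCF for lower facial volume carries only observed postbaseline values.
3. State that participants with no observed postbaseline volume are left out of the volume ANCOVA, and report the N used at each visit.
4. Keep the planned ANCOVA, and extend the observed-data sensitivity analysis of SAP 9.1 to volume under both area-of-interest methods.

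Optionally, add an MMRM on observed volumes, or multiple imputation by arm with Rubin's rules, as a further sensitivity analysis.

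The cost is SAP wording and minor programming. The protocol's ANCOVA and LOCF stay as they are, so no amendment and no extra participants are needed. Compared with the by-arm fill, the reported standard error widens from about 1.14 to 1.26 cm³ at 5 of 50 missing, or from 1.19 to 1.21 at 1 of 50 (assumed SD 6). The volume N may fall slightly below the mITT N.
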